**Table 7: Hematology Assessments**

Hematology Assessments
Hematocrit
Hemoglobin
HbA1C (Screening, Week 12)
Red blood cell (RBC) count
White blood cell (WBC) count
Neutrophils
Bands (if detected)
Lymphocytes
Monocytes
Basophils (if detected)
Eosinophils (if detected)
Absolute platelet count
Mean corpuscular hemoglobin (MCH)
Mean corpuscular volume (MCV)
Mean corpuscular hemoglobin concentration (MCHC)
Reticulocyte count

**9.9.17. Urinalysis and Microscopy**

Urine samples will be collected for urinalysis and microscopy assessments at the times indicated in Table 3, Table 4, and Table 5. Every effort should be made to collect laboratory data using the central lab. Where use of the central lab is not possible, laboratory assessments should be collected through a local lab and reviewed by the investigator. Urinalysis and microscopy assessments are listed in Table 8.

**Table 8: Urinalysis/Microscopy Assessments**

Urinalysis/Microscopy Assessments
Specific gravity
Ketones
pH
Protein
Blood
Glucose
Urobilinogen
Bilirubin
Microscopic examination (if indicated based on laboratory procedures)
Leukocytes
Nitrates

**9.9.18. N-Terminal Prohormone of B-Type Natriuretic Peptide and B-Type Natriuretic Peptide**

Blood samples will be collected for N-terminal prohormone of B-type natriuretic peptide (NT-proBNP) and BNP at the times indicated in Table 3, Table 4, and Table 5 (at the same time as the central lab blood collection). Every effort should be made to collect laboratory data using the central lab. Where use of the central lab is not possible, laboratory assessments should be collected through a local lab and reviewed by the investigator. Since NT-proBNP may be affected by recent exercise, patients must be allowed to rest for a minimum period of 1 hour following study-specific exercise testing prior to obtaining this blood sample. This sample

should be taken with the patient in the same position at all appropriate visits (e.g., sitting or semi-recumbent).

#### **9.9.19. Hepatitis B and C and Human Immunodeficiency Virus**

Blood samples will be collected for hepatitis B and C and HIV antibody assessments only in patients lacking evidence of a negative titer in the past year at the time indicated in [Table 3](#), [Table 4](#), and [Table 5](#).

#### **9.9.20. Pregnancy Test**

WOCBP (Section [9.7.1](#)) will provide a blood or urine sample for a pregnancy test at the times indicated in [Table 3](#), [Table 4](#), and [Table 5](#). Negative serum test results are required at the Screening Visit before study enrollment, and negative urine test results are required at all other times indicated in [Table 3](#), [Table 4](#), and [Table 5](#) for continued participation in the study. Any patient who becomes pregnant during the study must discontinue taking study drug immediately. See Section [9.7.3](#) for a description of procedures to be followed in case of pregnancy.

#### **9.9.21. Exercise Regimen Reporting**

Exercise regimen will be recorded at baseline. Patients will be asked about changes to their exercise regimen at the times indicated in [Table 3](#) and [Table 4](#). Changes to the exercise regimen during Part 1 or Part 2 will be recorded as protocol deviations.

#### **9.9.22. Study Drug Dispensation**

Enough study drug will be dispensed to the patient at the times indicated in [Table 3](#), [Table 4](#), and [Table 5](#) to last at least until the next study visit, along with instructions for use.

#### **9.9.23. Study Drug Return and Pill Count**

Study drug will be collected from the patient and pills will be counted by the principal investigator or the study staff at the times indicated in [Table 3](#), [Table 4](#), and [Table 5](#) to determine treatment compliance. Criteria for noncompliance and instructions for recording compliance on the CRF are included in Section [9.3](#).

Patients will be provided a dosing diary in Part 1 and Part 2 to track all doses administered, including the date and time of each dose. The patient will bring the dosing diary to the clinic to be reviewed by the site staff for study drug accountability.

#### **9.9.24. Study Drug Administration**

Part 1: As outlined in Section [9.1](#), study drug treatment kits will contain up to six 30-count bottles of RTA 408 or placebo capsules. Patients should take 1 capsule from each bottle daily. Patients should self-administer study drug orally once daily in the morning on an empty stomach (approximately 1 hour before or 2 hours after eating). Study drug should be taken with water at the times indicated in [Table 3](#), except on Days 1, 14, 56 (Cohort 1; Part 1 only), and 84, when study staff will administer study drug at the clinic following all assessments on Day 1, and after the pre-dose blood sample for PK analysis on Days 14, 56 (Cohort 1; Part 1 only), and 84. The date and time of the 2 most recent doses of study medication prior to Days 14, 56 (Cohort 1; Part 1 only), and 84 will be recorded for PK analysis. The date and time of the last study drug

administration (Day 84) should be recorded. A vomited dose should not be replaced. Missed doses may be taken in the afternoon or evening of the same day approximately 1 hour before or 2 hours after a meal. A double dose (e.g., missed dose from previous day and dose for current day) should not be taken.

Part 2: As outlined in Section 9.1, study drug treatment kits will contain three 30-count bottles of RTA 408 or placebo capsules. Patients should self-administer study drug orally once daily in the morning on an empty stomach (approximately 1 hour before or 2 hours after eating). Study drug should be taken with water at the times indicated in Table 4, except on Days 1, 14, 84, 168, and 336, when study staff will administer study drug at the clinic following all assessments on Day 1, and after the pre-dose blood sample for PK analysis on Days 14, 84, 168, and 336. The date and time of the 2 most recent doses of study medication prior to Days 14, 84, and 168, will be recorded for PK analysis. The date and time of the last study drug administration (Day 336) should be recorded.

Extension: As outlined in Section 9.1, patients will ingest 3 capsules daily throughout the study. Study drug should be taken with water at the times indicated in Table 5. Treatment kits containing RTA 408 will include 3 bottles, each containing 30 count of active (RTA 408 50 mg) capsules. Patients may receive more than 1 treatment kit during dispensation to provide sufficient study drug until their next planned dispensation.

A vomited dose should not be replaced. Missed doses may be taken in the afternoon or evening of the same day approximately 1 hour before or 2 hours after a meal. A double dose (e.g., missed dose from previous day and dose for current day) should not be taken.

#### **9.9.25. Telephone Contact**

Sites should complete a telephone visit contact with the patient to assess AEs and concomitant medications at the times indicated in Table 3, Table 4, and Table 5. Sites should make at least 3 attempts to contact the patient within the visit window if contact attempts are unsuccessful.

#### **9.9.26. Maximal Exercise Test**

Cycle ergometry using a recumbent stationary bicycle will be used to conduct maximal exercise testing at the times indicated in Table 3 and Table 4. An example of the procedures for maximal exercise testing is provided in Appendix 2. Procedures for maximal exercise testing will be included in a study manual. Maximal exercise testing assessments include but are not limited to peak work and peak oxygen utilization. On study days where multiple assessments are to be completed, the maximal exercise test must be the first functional assessment performed.

#### **9.9.27. Friedreich's Ataxia Rating Scale**

The examiner will complete the full FARS neurological examination on the patient at the times indicated in Table 3, Table 4, and Table 5. An example of the procedures for the FARS assessment is provided in Appendix 3. A practice FARS assessment is included in the schedule of assessments to familiarize those patients who have not recently completed a FARS assessment with the components of the neurological exam. The practice FARS assessment is not required for patients having completed a FARS assessment within 90 days prior to Screening. The practice FARS assessment must be performed prior to the screening maximal exercise test.

Other than the practice FARS, all FARS neurological examinations must be performed following maximal exercise testing.

The examiner will need a reflex hammer, tuning fork, and stopwatch. Instructions will be provided in the study manual. The FARS examination should be completed by one of the neurologists at the site delegated to complete this assessment. The individual components of this examination will be recorded so that the mFARS score can be calculated as a subset of the full neurological FARS examination score, as required.

The full neurologic FARS is divided into 5 sections: bulbar, upper limb coordination, lower limb coordination, peripheral nervous system, and upright stability. This examination must be performed and ratings determined by a trained neurologist. As the examiner proceeds through the items, he/she can call out scores to a coordinator or research assistant to record onto the CRF.

For every item in the FARS exam, a higher score means that the patient is more severely affected. A score of 0 for an item means that the patient has a normal score. Not all of the items have the same possible scoring range. Some of the items will range from 0 to 2, while others will range from 0 to 4. Some items can be scored with 0.5 increments if the examiner feels that the patient falls between 2 defined scoring severities. There are specific instructions for performing assessment of each item and scoring instructions on the CRF.

The mFARS is not a separate assessment, but rather calculated as the full FARS neurological assessment minus section D (peripheral nervous system). The mFARS includes 4 sections: bulbar, upper limb coordination, lower limb coordination, and upright stability.

#### **9.9.28. 9-Hole Peg Test**

Patients will take the 9-HPT ([Appendix 4](#)) at the times indicated in Table 3, Table 4, and Table 5. Instructions are provided in the study manual.

#### **9.9.29. 25-Foot Timed Walk Test**

Ambulatory patients will complete the 25-foot timed walk test at the times indicated in [Table 3](#), [Table 4](#), and [Table 5](#). If a patient uses an assistive device for the 25-foot timed walk test on Day 1, the same assistive device must be used for all 25-foot walk assessments. Patients will have the option to consent to video recording during the 25-foot timed walk test at selected sites. Video recording for the 25-foot timed walk test is optional. Procedures for video collection will be described in a separate study-specific manual.

#### **9.9.30. Video Collection of Patients Walking 25-ft with Their Natural Gait**

Patients who consent to video collection of the 25-foot timed walk test will also have video collection during normal walking with a 25-foot (un-timed) walk using his/her normal gait, at the times indicated in Table 4. The normal walk must be performed after the 25-foot timed walk test. Procedures for video collection will be described in a separate study specific manual.

#### **9.9.31. SF-36 Health Survey Update**

Patients will be instructed to answer the 36 questions on the SF-36 survey ([Jenkinson, 1999](#)) according to how they have felt over the previous week, at the times indicated in Table 3 and Table 4. The SF-36 ([Appendix 5](#)) assesses 8 health concepts: (1) limitations in physical

activities because of health problems; (2) limitations in social activities because of physical or emotional problems; (3) limitations in usual role activities because of physical health problems; (4) bodily pain; (5) general mental health (psychological distress and well-being); (6) limitations in usual role activities because of emotional problems; (7) vitality (energy and fatigue); and (8) general health perceptions.

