**2. Compared to one year ago, how would you rate your health in general now?**

Much better now than one year ago	Somewhat better now than one year ago	About the same as one year ago	Somewhat worse now than one year ago	Much worse now than one year ago
▼	▼	▼	▼	▼
 1	 2	 3	 4	 5

**3. The following questions are about activities you might do during a typical day. Does your health now limit you in these activities? If so, how much?**

Yes, limited a lot	Yes, limited a little	No, not limited at all
▼	▼	▼

- a Vigorous activities, such as running, lifting heavy objects, participating in strenuous sports .....  1 .....  2 .....  3
- b Moderate activities, such as moving a table, pushing a vacuum cleaner, bowling, or playing golf.....  1 .....  2 .....  3
- c Lifting or carrying groceries .....  1 .....  2 .....  3
- d Climbing several flights of stairs .....  1 .....  2 .....  3
- e Climbing one flight of stairs .....  1 .....  2 .....  3
- f Bending, kneeling, or stooping .....  1 .....  2 .....  3
- g Walking more than a mile.....  1 .....  2 .....  3
- h Walking several hundred yards .....  1 .....  2 .....  3
- i Walking one hundred yards .....  1 .....  2 .....  3
- j Bathing or dressing yourself .....  1 .....  2 .....  3

**4. During the past 4 weeks, how much of the time have you had any of the following problems with your work or other regular daily activities as a result of your physical health?**

All of the time	Most of the time	Some of the time	A little of the time	None of the time
▼	▼	▼	▼	▼

- a Cut down on the amount of time you spent on work or other activities.....  1 .....  2 .....  3 .....  4 .....  5
- b Accomplished less than you would like .....  1 .....  2 .....  3 .....  4 .....  5
- c Were limited in the kind of work or other activities .....  1 .....  2 .....  3 .....  4 .....  5
- d Had difficulty performing the work or other activities (for example, it took extra effort) .....  1 .....  2 .....  3 .....  4 .....  5

**5. During the past 4 weeks, how much of the time have you had any of the following problems with your work or other regular daily activities as a result of any emotional problems (such as feeling depressed or anxious)?**

All of the time	Most of the time	Some of the time	A little of the time	None of the time
▼	▼	▼	▼	▼

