- a Cut down on the amount of time you spent on work or other activities.....  1 .....  2 .....  3 .....  4 .....  5
- b Accomplished less than you would like .....  1 .....  2 .....  3 .....  4 .....  5
- c Did work or other activities less carefully than usual .....  1 .....  2 .....  3 .....  4 .....  5

**6. During the past 4 weeks, to what extent has your physical health or emotional problems interfered with your normal social activities with family, friends, neighbors, or groups?**

Not at all	Slightly	Moderately	Quite a bit	Extremely
▼	▼	▼	▼	▼
 1	 2	 3	 4	 5

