**7. How much bodily pain have you had during the past 4 weeks?**

None	Very mild	Mild	Moderate	Severe	Very severe
▼	▼	▼	▼	▼	▼
 1	 2	 3	 4	 5	 6

**8. During the past 4 weeks, how much did pain interfere with your normal work (including both work outside the home and housework)?**

Not at all	A little bit	Moderately	Quite a bit	Extremely
▼	▼	▼	▼	▼
 1	 2	 3	 4	 5

**9. These questions are about how you feel and how things have been with you during the past 4 weeks. For each question, please give the one answer that comes closest to the way you have been feeling. How much of the time during the past 4 weeks...**

All of the time	Most of the time	Some of the time	A little of the time	None of the time
▼	▼	▼	▼	▼

- a Did you feel full of life? .....  1 .....  2 .....  3 .....  4 .....  5
- b Have you been very nervous? .....  1 .....  2 .....  3 .....  4 .....  5
- c Have you felt so down in the  
dumps that nothing could  
cheer you up? .....  1 .....  2 .....  3 .....  4 .....  5
- d Have you felt calm and  
peaceful? .....  1 .....  2 .....  3 .....  4 .....  5
- e Did you have a lot of energy? .....  1 .....  2 .....  3 .....  4 .....  5
- f Have you felt downhearted  
and depressed? .....  1 .....  2 .....  3 .....  4 .....  5
- g Did you feel worn out? .....  1 .....  2 .....  3 .....  4 .....  5
- h Have you been happy? .....  1 .....  2 .....  3 .....  4 .....  5
- i Did you feel tired? .....  1 .....  2 .....  3 .....  4 .....  5

**10. During the past 4 weeks, how much of the time has your physical health or emotional problems interfered with your social activities (like visiting with friends, relatives, etc.)?**

All of the time	Most of the time	Some of the time	A little of the time	None of the time
▼	▼	▼	▼	▼
 1	 2	 3	 4	 5

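### Section 9.9.31 has patients answer all 36 SF-36 questions for the previous week, but 20 of the 36 items on the Appendix 5 form ask about the past 4 weeks and none asks about one week

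*Protocol*

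**What the plan says.** Protocol Section 9.9.31 sets the procedure for both parts: "Patients will be instructed to answer the 36 questions on the SF-36 survey", and to do so "according to how they have felt over the previous week". The instruction covers the full questionnaire and makes no exception for individual items. The same section identifies the form as the one in Appendix 5 and the visits as those in Tables 3 and 4.

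The form states a different period. Question 4 begins "During the past 4 weeks, how much of the time have you had any of the following problems with your work", and question 5 opens in the same way. Question 6 reads "During the past 4 weeks, to what extent has your physical health or emotional problems interfered". The two pain questions read "How much bodily pain have you had during the past 4 weeks" and "During the past 4 weeks, how much did pain interfere with your normal work". Question 9 is introduced by "These questions are about how you feel and how things have been with you during the past 4 weeks", and question 10 also refers to the past 4 weeks.

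The SF-36 is listed among the exploratory objectives in Sections 6.1.3 (Part 1) and 6.2.3 (Part 2). Section 11.1.7 analyses the change from baseline to Week 12, and Section 11.2.7 the change at Weeks 24 and 48.

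**The concern.** The sentence in 9.9.31 is operational: it says what patients are to be told. A site that follows it gives an instruction that disagrees with the page in front of the patient. A site that simply hands over the form collects answers for 4 weeks. Both could claim to be following the protocol.

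Two things are at stake. First, if sites took different routes, the pooled SF-36 scores would rest on two recall periods. Second, if every site followed the text, the scores would be uniform but would no longer be those of the instrument as Appendix 5 prints it, which makes them harder to interpret. Part 1 is exposed as well as Part 2, because the same sentence governs both schedules.

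**Working it through.** No sample size, power or error rate is involved, so the check is a comparison of texts and a count of items.

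**Step 1: recall period by question, read from Appendix 5.**

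| Question | Items | Period on the form |
|---|---|---|
| 1 | 1 | none stated |
| 2 | 1 | comparison with one year ago |
| 3 | 10 | a typical day, now |
| 4 | 4 | past 4 weeks |
| 5 | 3 | past 4 weeks |
| 6 | 1 | past 4 weeks |
| 7 | 1 | past 4 weeks |
| 8 | 1 | past 4 weeks |
| 9 | 9 | past 4 weeks |
| 10 | 1 | past 4 weeks |
| 11 | 4 | none stated |

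**Step 2: totals.**

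- All items: 1 + 1 + 10 + 4 + 3 + 1 + 1 + 1 + 9 + 1 + 4 = 36, which agrees with the number given in 9.9.31.
- Items worded for the past 4 weeks: 4 + 3 + 1 + 1 + 1 + 9 + 1 = 20, and 20/36 = 56%.
- Remaining items: 1 + 1 + 10 + 4 = 16. Of these, 15 (questions 1, 3 and 11) carry no dated recall period, and 1 (question 2) looks back one year.
- Items worded for one week: 0.

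The one-week instruction therefore matches no item on the form. It contradicts 20 items outright and does not fit question 2 either.

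**Step 3: does anything reconcile the two?** Section 9.9.31 points to no study manual, whereas the sections on the 9-hole peg test (9.9.28) and the visual acuity test (9.9.38) do. Section 9.9.39 gives the Fatigue Severity Scale a past-week recall, so the protocol sets recall periods instrument by instrument, and that statement cannot be carried over to the SF-36. The supplied SAP document deals only with what replaces site as a covariate when data are sparse. Both protocol texts are complete and current, with nothing blacked out at this point.

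**Step 4: where could it act?** Table 3 schedules the SF-36 at Day 1 and Week 12, and Table 4 at Day 1, Week 24 and Week 48. Table 5 (extension) does not include it. Appendix 13 states that Parts 1 and 2 had been completed by the time of the pandemic, so under this version no SF-36 assessment remains to be done.

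**The case against.** The strongest reply is that the form governs in practice. It is a written questionnaire addressed to the patient, and the 4-week period is printed in the question wording or lead-in for all 20 items. If patients answered what they read, the data are uniform and only a protocol sentence is wrong. The documents do not exclude this, so mixed recall can be stated only as a possibility.

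A reader might go further and infer that change from baseline does mix recall periods, even within a patient. The documents do not support that. Nothing shows that any site gave a one-week instruction or that sites differed. The sentence and the form are the same at every visit, and Section 9.9 asks for every effort to have one individual complete all of a patient's assessments. A site that consistently followed either source would give each patient one recall period throughout, and change from baseline would compare like with like.

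A reader might also infer a biased treatment comparison. Both parts are randomized and double-blind (Sections 7.1 and 9.5), so a site's habit of instruction has no evident route to differ systematically by arm. The plausible cost is noise and unclear interpretation.

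It is also fair to say that 20 of 36 measures disagreement in wording. It does not say how far any score would move.

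What remains after all this is the contradiction itself. A rule for administering the instrument conflicts with the instrument, and a site that obeyed it would have departed from the form.

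**Conclusion.** The inconsistency is real and can be confirmed by reading two places in the protocol: 20 of 36 items (56%) contradict the instructed recall period, and none agrees with it. Its consequence is conditional. Only if sites applied the text could SF-36 scores mix recall periods between sites or depart from the printed instrument.

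The importance is low. The endpoint is exploratory in both parts, and neither the primary nor the secondary endpoints, nor power, nor type I error is touched. The effect in score points cannot be estimated, because the documents give no data on how SF-36 answers vary with recall period.

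The conclusion assumes that Appendix 5 reproduces the form patients completed, and that no site instruction outside the supplied documents settled the matter.

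**What to change.** In Section 9.9.31, replace "according to how they have felt over the previous week" with a reference to the recall period printed for each item on the Appendix 5 form. This is one sentence of text and changes no procedure, visit, sample size or analysis.

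Because the SF-36 data have already been collected, the correction alone cannot alter any answer. The sponsor should therefore also establish from site records which recall instruction patients actually received in Parts 1 and 2, document it, and report it with the SF-36 results. If sites differed, or the records cannot settle the question, the report should say so. The cost is a query to sites and a short statement in the study report.
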